## **Renal Adverse Event Management Algorithm**

[figure not shown]
Rule out non-inflammatory causes. If non-inflammatory cause, treat accordingly and continue I-O therapy

Patients on IV steroids may be switched to an equivalent dose of oral corticosteroids (e.g. prednisone) at start of tapering or earlier, once sustained clinical improvement is observed. Lower bioavailability of oral corticosteroids should be taken into account when switching to the equivalent dose of oral corticosteroids.

# **Endocrinopathy Management Algorithm**

[figure not shown]
Rule out non-inflammatory causes. If non-inflammatory cause, treat accordingly and continue I-O therapy. Consider visual field testing, endocrinology consultation, and imaging.

Patients on IV steroids may be switched to an equivalent dose of oral corticosteroids (e.g. prednisone) at start of tapering or earlier, once sustained clinical improvement is observed. Lower bioavailability of oral corticosteroids should be taken into account when switching to the equivalent dose of oral corticosteroids.

# **Skin Adverse Event Management Algorithm**

[figure not shown]
Rule out non-inflammatory causes. If non-inflammatory cause, treat accordingly and continue I-O therapy.

Patients on IV steroids may be switched to an equivalent dose of oral corticosteroids (e.g., prednisone) at start of tapering or earlier, once sustained clinical improvement is observed. Lower bioavailability of oral corticosteroids should be taken into account when switching to the equivalent dose of oral corticosteroids. \*Refer to NCI CTCAE v4 for term-specific grading criteria.

# **Pulmonary Adverse Event Management Algorithm**

[figure not shown]
Rule out non-inflammatory causes. If non-inflammatory cause, treat accordingly and continue I-O therapy. Evaluate with imaging and pulmonary consultation.

Patients on IV steroids may be switched to an equivalent dose of oral corticosteroids (e.g. prednisone) at start of tapering or earlier, once sustained clinic: improvement is observed. Lower bioavailability of oral corticosteroids should be taken into account when switching to the equivalent dose of oral corticosteroids.

## **Hepatic Adverse Event Management Algorithm**

Rule out non-inflammatory causes. If non-inflammatory cause, treat accordingly and continue I-O therapy. Consider imaging for obstruction.

[figure not shown]

Patients on IV steroids may be switched to an equivalent dose of oral corticosteroids (e.g. prednisone) at start of tapering or earlier, once sustained clinical improvement is observed. Lower bioavailability of oral corticosteroids should be taken into account when switching to the equivalent dose of oral corticosteroids. \*I-O therapy may be delayed rather than discontinued if AST/ALT ≤ 8 x ULN and T.bili ≤ 5 x ULN.

\*\*The recommended starting dose for grade 4 hepatitis is 2 mg/kg/day methylprednisolone IV.

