# 7.3 Withdrawal, Removal, and Replacement of Participants

A participant may voluntarily withdraw or be withdrawn from the study at any time for reasons including, but not limited to, the following:

- Progression of disease: Either unequivocal symptomatic progression necessitating a change in therapy in the opinion of the treating physician or radiologic progression as defined by cross-sectional imaging utilizing RECIST 1.1 criteria.
- Treatment Cessation: Discontinuation criteria apply for all drug-related AEs attributed to nivolumab, ipilimumab or both. Treatment with all study drugs should be permanently discontinued for the following:
  - Any Grade 2 drug related uveitis or eye pain or blurred vision that does not respond to topical therapy and does not improve to Grade 1 severity within the re-treatment period OR requires systemic treatment
  - o Any Grade 3 non-skin, drug-related AE, with the following exceptions:
    - Grade 3 diarrhea lasting <7 days
    - Grade 3 drug-related laboratory abnormalities do not require treatment discontinuation except
      - ➤ Grade 3 drug-related thrombocytopenia >7 days or associated with bleeding requires discontinuation
      - Any drug-related liver function test abnormality that meets the following criteria requires discontinuation:
        - AST or ALT >8 x upper limit of normal (ULN)
        - Total Bilirubin >5x ULN
        - Concurrent AST or ALT and total bilirubin >2x ULN
  - Any Grade 4 drug-related AE or laboratory abnormality, except for the following events which do not require discontinuation.

- Grade 4 amylase or lipase abnormalities that are not associated with symptoms or clinical manifestations of pancreatitis.
- Isolated Grade 4 electrolyte imbalances/abnormalities that are not associated with clinical sequelae and are corrected with supplementation/appropriate management within 72 hours of their onset
- Any dosing interruption lasting >6 weeks with the following exceptions:
  - Dosing interruptions to allow for prolonged steroid tapers to manage drugrelated AEs are allowed.
  - Dosing interruptions >6 weeks that occur for non-drug related may be allowed if approved by the primary Investigator
- Any AE, laboratory abnormality or intercurrent illness which, in the judgment of the Investigator, presents a substantial clinical risk to the participant with continued drug dosing.
- Withdrawal of consent: Participant may withdraw consent at any time.
- Death

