## 8.4.2 Monitoring and Dose Delay Criteria

Participants should be assessed for toxicity prior to each dose; dosing will occur only if the clinical assessment and laboratory test values are acceptable. If toxicity occurs as indicated below, participants in both study arms should have study drug(s) held. In participants who are in the combined treatment arm, both drugs should be held for any toxicity. Dose delays are designed to maximize treatment for those who derive clinical benefit from treatment while ensuring participant safety. Participants should follow timed assessments, and continuation on study is at the PI's discretion.

Nivolumab and/or ipilimumab administration should be delayed for the following reasons:

- Grade ≥2 non-skin, drug-related AEs with the following exceptions:
  - Grade 2 drug-related fatigue or laboratory abnormalities do not require a treatment delay
- Any Grade 3 skin, drug-related AE
- Any Grade 3 drug-related laboratory abnormalities with the following exceptions for lymphopenia, leukopenia, AST, ALT or total bilirubin
  - o Grade 3 lymphopenia or leukopenia does not require dose delay
  - o If a participant has a baseline AST, ALT or total bilirubin that is within normal limits, delay dosing for drug-related Grade ≥2 toxicity
  - If a participant has a baseline AST, ALT or total bilirubin that is within the Grade 1 toxicity range, delay dosing for drug-related Grade ≥3 toxicity
- Any AE, laboratory abnormalities, or intercurrent illness, which in the judgment of the Investigator warrants delaying the dose of study drug.

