#### 8.4.3 Management Algorithms for Immune-related Adverse Events

Immuno-oncology agents are associated with AEs that can differ in severity and duration from AEs caused by other therapeutic classes. Early recognition and management of AEs associated with immuno-oncology agents may mitigate severe toxicity. Immune-related AEs will be managed as per published guidelines. Please see Appendix 2 for further details.

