# 8.4.4 Dose Modifications

Nivolumab and ipilimumab dose reductions and escalations are not permitted in either study arm.

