### 15.2 Appendix 2: Management Algorithms for Immuno-Oncology Agents

Immuno-oncology (I-O) agents are associated with AEs that can differ in severity and duration than AEs caused by other therapeutic classes. Nivolumab and ipilimumab are considered immuno-oncology agents in this protocol. Management algorithms have been developed to assist investigators in assessing and managing the following groups of AEs: Gastrointestinal, Renal, Pulmonary, Hepatic, Endocrinopathies, Skin, and Neurological.

Early recognition and intervention are recommended according to the management algorithms; and in addition include ophthalmologic evaluations for any visual symptoms in order to evaluate for nivolumab or ipilimumab related uveitis.

The recommendations are to follow the algorithms in the nivolumab IB for immune related events; while the ipilimumab IB contains similar algorithms, the algorithms in the nivolumab brochure have been aligned to accommodate combinations as well as nivolumab monotherapy.

[figure not shown]
Therefore, the algorithms recommended for utilization are attached for reference. For participants expected who require more than 4 weeks of corticosteroids or other immunosuppressants to manage an AE, consider the following recommendations.

- Antimicrobial/antifungal prophylaxis per institutional guidelines to prevent opportunistic infections such as *Pneumocystis jiroveci* and fungal infections.
- Early consultation with an infectious disease specialist should be considered. Depending on the presentation, consultation with a pulmonologist for bronchoscopy or a gastroenterologist for endoscopy may also be appropriate.
- In participants who develop recurrent AEs in the setting of ongoing or prior immunosuppressant use, an opportunistic infection should be considered in the differential diagnosis.

Additional details on the safety of nivolumab and ipilimumab, including results from clinical studies, are available in the IB.

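### The Appendix 2 hepatic footnote allows delay for some combined AST/ALT and bilirubin elevations that Protocol Section 7.3 says must stop treatment, and the dosing sections do not say that 7.3 prevails

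*Protocol*

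**What the plan says.** Protocol Section 7.3, under treatment cessation, states: "Treatment with all study drugs should be permanently discontinued for the following". For drug-related liver tests it names three criteria: AST or ALT above 8x ULN; total bilirubin above 5x ULN; and "Concurrent AST or ALT and total bilirubin >2x ULN".

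The hepatic algorithm in Appendix 2 carries a footnote: "I-O therapy may be delayed rather than discontinued if AST/ALT ≤ 8 x ULN and T.bili ≤ 5 x ULN". The introduction to Appendix 2 describes the status of these flowcharts: "the algorithms recommended for utilization are attached for reference".

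The dosing text lies between the two. Section 8.4.2 says: "If a participant has a baseline AST, ALT or total bilirubin that is within normal limits, delay dosing for drug-related Grade" 2 or higher toxicity; the trigger is Grade 3 or higher if the baseline value was in the Grade 1 range. Section 8.4.3 says: "Immune-related AEs will be managed as per published guidelines. Please see Appendix 2 for further details". Section 8.4.5 allows dosing to resume once a drug-related event has settled to Grade 1 or below or to baseline, with listed exceptions, and again points to Appendix 2. None of these three sections refers to 7.3. Section 8.4.4 adds: "Nivolumab and ipilimumab dose reductions and escalations are not permitted in either study arm".

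**The concern.** The footnote's two limits are the exact complement of the first two stop criteria in 7.3, so it looks written to agree with them. The third criterion, combined elevation at lower levels, has no counterpart. A site that manages a liver event from Section 8.4 is led to Appendix 2, not to 7.3, and could read the footnote as permission to hold and later re-dose someone whom 7.3 says must stop. With dose reductions barred, re-dosing would be at full dose.

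The other safeguards lower this risk without removing it:

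- The drug-induced liver injury definition in Section 11.1.2 (AST or ALT above 3x with bilirubin above 2x ULN) triggers reporting, not a stop. It does not cover cases with raised alkaline phosphatase or another apparent cause.
- The 6-week limit on dosing interruptions in 7.3 has an exception: "Dosing interruptions to allow for prolonged steroid tapers to manage" drug-related events. It need not catch a liver event treated with steroids.
- Section 7.3 lets the investigator stop for substantial clinical risk, but that is a judgement.
- The Data Review Team (Section 12.5) has no stated meeting interval. Section 13.6 adds remote monitoring, site visits every 16 weeks and routine medical review of participant-level data. With cycles of 21 days, a re-dose could come before a site visit.

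**Working it through.** The plan gives no figure to reproduce, so the check sets the two rules against each other. Let A be AST or ALT and B total bilirubin, both as multiples of ULN.

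**Rules**

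- Stop (7.3, drug-related): A > 8, or B > 5, or (A > m and B > 2).
- Delay allowed (Appendix 2 footnote): A ≤ 8 and B ≤ 5.

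The 7.3 line does not make clear which multiple m applies to AST/ALT. The plain reading is m = 2 for both tests. As sensitivity values I also took m = 1 (any elevation), m = 3 (the liver-injury cut-off in 11.1.2) and m = 5 (the eligibility ceiling with liver metastases, inclusion criterion 9f). Only the multiple of 2 is printed in the 7.3 line; the other three are assumptions.

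**Step 1, first two criteria.** A > 8 or B > 5 is the logical opposite of A ≤ 8 and B ≤ 5. The overlap is empty.

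**Step 2, concurrent criterion.** Stop and delay both hold when m < A ≤ 8 and 2 < B ≤ 5. This region is not empty for any of the four values of m.

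| A | B | 7.3 requires stop | Footnote allows delay | Conflict |
|---|---|---|---|---|
| 9 | 1 | yes | no | no |
| 6 | 1.5 | no | yes | no |
| 4 | 3 | yes for m = 1, 2, 3; no for m = 5 | yes | for m = 1, 2, 3 |
| 6 | 3 | yes for all four | yes | yes |

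The case A = 6, B = 3 conflicts whichever multiple is meant, so the finding does not depend on that ambiguity.

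**Step 3, the unseen flowchart box.** The footnote qualifies a box that is not shown. If that box covered only severe elevations, say A > 5 or B > 3 (an assumption, not in the documents), A = 6, B = 3 would still fall inside it because 6 > 5. A separate box for combined elevation would remove the conflict, and that cannot be excluded.

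**Step 4, doses at stake.** Treatment is 4 doses. After onset following dose k, 4 − k remain.

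| Onset after dose k | Doses left | Ipilimumab, 3 mg/kg × (4 − k) | Nivolumab in Arm A, 1 mg/kg × (4 − k) |
|---|---|---|---|
| 1 | 3 | 9 mg/kg | 3 mg/kg |
| 2 | 2 | 6 mg/kg | 2 mg/kg |
| 3 | 1 | 3 mg/kg | 1 mg/kg |
| 4 | 0 | 0 | 0 |

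The first row is a worst case: onset after the first dose, then recovery, then every remaining dose given.

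**The case against.** The strongest reply is that a mandatory rule and an advisory note do not truly clash. Section 7.3 says its discontinuation criteria cover all drug-related events attributed to either drug, and it uses the language of requirement. Appendix 2 exists to help investigators, and its footnote only permits. A site that stops complies with both texts. This stands, and it is why 7.3 should be taken as governing. What it leaves open is that the protocol expects the reader to infer this, in the sections where the dosing decision is made.

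The second reply is that the footnote belongs to a figure that cannot be seen here. This also stands. The point is confined to the footnote's wording, and a reader should not conclude that the full algorithm says nothing about combined elevation. A sentence on precedence would be correct whatever the figure shows.

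Third, harm needs a chain of events: a site overlooks 7.3, relies on the footnote, sees recovery, and re-doses. A reader might infer that 8.4.5 authorises re-dosing after a 7.3 stop. It does not: it ends holds made under 8.4.2 and does not reopen a permanent discontinuation. It matters only if the site has already treated the event as a delay. The check before each dose in 8.4.2 helps, but recovered values could pass it.

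**Conclusion.** The inconsistency is real but narrow. For drug-related events with bilirubin above 2x and up to 5x ULN, and AST/ALT above the applicable multiple and up to 8x ULN, the footnote's wording allows a delay where 7.3 requires a stop. Sections 8.4.3 and 8.4.5 point sites to the footnote without mentioning 7.3.

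The documents do not support the stronger reading that the protocol authorises re-dosing after combined liver injury, or that 7.3 is overridden. The only precedence statement, in Section 12, places the SAP above the protocol and does not bear on this.

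The exposure at stake is at most 3 doses per affected participant. The documents give no rate for such events; among 24 participants I would expect few, but that is a judgement. Sample size and the primary analysis do not change. This is a safety clarification worth making, held with medium confidence because the flowchart is not visible.

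**What to change.** Add one sentence to Section 8.4.3, repeated at the head of Appendix 2: the permanent discontinuation criteria in Section 7.3, including the concurrent AST/ALT and bilirubin criterion, prevail over the Appendix 2 algorithms.

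A clause in the footnote excepting the concurrent criterion is optional. Appendix 2 takes its recommended algorithms from the nivolumab Investigator's Brochure, so editing the footnote could make the attached copy differ from its source. The precedence sentence avoids that.

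No change to the 7.3 threshold is proposed. The clinical team could usefully state which AST/ALT multiple the concurrent line means, since participants with liver metastases may enter with values up to 5x ULN.

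The cost is a formal amendment submitted to the IRB/IEC, which Section 13.8.1 requires even for clarifications. A participant who recovers loses the remaining doses, at most 3, as 7.3 already requires. If dosing has finished, the useful step is to check recorded hepatic events against the 7.3 criteria and report any re-dosing that they ruled out.

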# **GI Adverse Event Management Algorithm**

Rule out non-inflammatory causes. If non-inflammatory cause is identified, treat accordingly and continue I-O therapy. Opiates/narcotics may mask symptoms of perforation. Infliximab should not be used in cases of perforation or sepsis.

Patients on IV steroids may be switched to an equivalent dose of oral corticosteroids (e.g. prednisone) at start of tapering or earlier, once sustained clinical improvement is observed. Lower bioavailability of oral corticosteroids should be taken into account when switching to the equivalent dose of oral corticosteroids.

.

### 15.3 Appendix 3: Laboratory Procedures

A variety of factors that could potentially predict clinical response to ipilimumab alone or in combination with nivolumab will be investigated in peripheral blood and in tumor specimens taken both pre- and post-treatment. All samples collected and banked may also be used for future exploratory analyses.

All sites will send samples, collected in the kits that are provided by Parker Institute for Cancer Immunotherapy, to a centralized biorepository location. The samples will be shipped from the biorepository to a centralized testing location for analysis. Sites will not be required to do any exploratory testing unless they have been identified as a testing site and the budgeting for that will be established separately.

### **Tumor tissue specimens**

Pre- and on- treatment tumor specimens will be obtained on all eligible participants. Tumor specimens collected may include (1) 4 core biopsy specimens or (2) an excision biopsy or (3) a specimen from surgical resection of a tumor. In the case of the core biopsy specimens, 3 core biopsies will be snap frozen and 1 biopsy will be formalin fixed and preserved in paraffin embedded blocks (FFPE). In the case of excisional or surgical specimens, approximately ½ of the specimen will be snap frozen and the other ½ will be formalin fixed and paraffin embedded.

### **Analysis of immune infiltrate**

Analysis of immune infiltrate will be performed using IHC and/or flow cytometry. Populations of cells analyzed may include, but will not be limited to, CD4, CD8, Treg populations, B cells, MDSC, monocytes, dendritic cells and expression of biologically relevant/phenotypic markers thereof. Standard established institutional protocols will be applied. Changes to these methods may be adapted depending upon the most recent, generally accepted protocols.

### **PD-L1 Expression**

PD-L1 expression will be assessed on both pre-treatment and on-treatment tumor biopsies in the form of formalin fixed paraffin embedded block or unstained slides. PD-L1 stained tissue sections will be assessed by a pathologist and membranous PD-L1 expression scored in tumor and immune cells. PD-L1 expression will be graded as positive for negative, according to the most up to date standards for the assay in use. Changes to these methods may be adapted depending upon the most recent, generally accepted protocols.

#### **Gene Expression Profiling:**

Gene expression profiling on tumor samples will be run using different methodologies. Genes of interest include but are not limited to cell surface makers such as CD4 and CD8, checkpoint molecules such as LAG3 and genes relevant to the interferon pathway. Standard established institutional protocols will be applied. Changes to these methods may be adapted depending upon the most recent, generally accepted protocol.

#### **RNA and DNA Preparation**

Core biopsies will be used to extract DNA or RNA. Whole blood samples will be collected in a lavender top tube for purification of RNA/DNA. Standard established institutional protocols will be applied. Changes to the methods for RNA and DNA preparation may be adapted depending upon the most recent, generally accepted protocols.

#### Exome sequencing of Tumor DNA and matched Normal DNA from Blood

Exome sequencing will be carried out on Illumina Hiseq 2100 to a mean target coverage of 150X using 500 ng of genomic DNA from frozen tissue as input. Changes to the methods for exome sequencing may be adapted depending upon the most recent, generally accepted protocols.

#### Transcriptome Sequencing of Tumor RNA

RNA-Seq analysis will be performed on samples with sufficient material. Sequencing libraries will be prepared from total RNA with the Illumina TruSeq mRNA library kit (v2) and then sequenced on the HiSeq 2500 with 2x50bp paired reads, yielding 47-60M reads per sample. The RNA reads will be aligned using the STAR aligner after which Cufflinks was used for gene quantification (FPKM). Changes to these methods may be adapted depending on the most recent, generally accepted protocols.

#### **Somatic Mutation Identification and Verification**

Raw sequencing data will be mapped to the human reference genome. Alignment, base-quality score recalibration, duplicate-read removal, and exclusion of germline variants will be performed using the Genome Analysis Toolkit (GATK). Known single nucleotide polymorphisms will be eliminated. Mutations will be annotated using SnpEffect, called with Somatic Sniper, VarScan, Strelka and MuTect then filtered and manually reviewed using IGV. Insertion and deletions (indels) will be called using Strelka.

Changes to these methods may be adapted depending on the most recent, generally accepted protocols.

#### **Neoantigen Prediction**

For each somatic SNV appearing in expressed genes, reference and mutated peptide sequences are generated. Each variant is linked to its corresponding coding DNA sequence (CDS) from Ensembl based on its B37 coordinates. The CDS is re-translated with the mutated DNA residue producing the mutated peptide product. NetMHCCons v1.1 generates a predicted binding affinity for all 8 to 11mers containing the mutated amino acid and all peptides with an IC50 score below 500nM are considered predicted neoepitopes. Changes to these methods may be adapted depending upon the most recent, generally accepted protocols.

